5.2. Exclusion Criteria

Participants are excluded from the study if any of the following criteria apply:

Medical Conditions

1. Have developed clinical evidence of significant, unstable or uncontrolled, acute or chronic diseases not due to SLE (i.e., cardiovascular, pulmonary, hematologic, gastrointestinal, hepatic, renal, neurological, malignancy or infectious diseases), or experienced an AE in 213560 study that could, in the opinion of the principal investigator, put the participant at undue risk.
2. Have developed any other medical diseases (e.g., cardiopulmonary), laboratory abnormalities, or conditions that, in the opinion of the principal investigator, makes the participant unsuitable for the study.
3. Have an estimated glomerular filtration rate as calculated by Schwartz Formula of less than 30 mL/min.
4. Have an IgA deficiency (IgA level <10 mg/dL).
5. Have a Grade 3 or greater laboratory abnormality based on the protocol toxicity scale (Section 10.2.1) except for the following that are allowed:
 - a) Stable Grade 3 hypoalbuminemia due to lupus nephritis and not related to liver disease or malnutrition.
 - b) Any grade proteinuria
 - c) Stable Grade 3 gamma glutamyl transferase (GGT) elevation due to lupus hepatitis and not related to alcoholic liver disease, uncontrolled diabetes or viral hepatitis. If present, any abnormalities in the alanine transaminase (ALT) and/or aspartate aminotransferase (AST) must be ≤Grade 2.
 - d) Stable Grade 3 neutropenia; or stable Grade 3 lymphopenia; or stable Grade 3 leukopenia, due to SLE

Diagnostic Assessments

6. Developing a positive test for HIV antibody after inclusion into 213560, per investigator's discretion according to clinical need.
7. Developing hepatitis B: Serologic evidence of Hepatitis B (HB) infection defined as Hepatitis B surface antigen positive (HBsAg+) OR Hepatitis B core antibody positive (HBcAb+) after inclusion into 213560, per investigator's discretion according to clinical need.
8. Developing a positive test for Hepatitis C antibody after inclusion into 213560, per investigator's discretion according to clinical need.

Prior/Concomitant Therapy

9. Have received a live or live-attenuated vaccine within 30 days of Day 1.

Other Exclusions

10. Are unable or unlikely, in the opinion of the investigator, to administer belimumab by SC injection and have no reliable source to administer the injection.

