#### **4.3.3. Additional Safety Assessments**

##### **4.3.3.1. Laboratory Data**

Laboratory Data including 12-week on-treatment period and 8-week post-treatment follow-up period will be included in the analysis.

Descriptive statistics for each analyte will be displayed for each week. The tables will display the mean value, standard deviation, median, 25th and 75th percentiles, minimum and maximum. No statistical tests will be performed.

A line graph will be produced for each analyte which displays the mean value by week.

Change from baseline for each analyte will also be summarized for each post-baseline week. The tables will display the mean value, standard deviation, median, 25th and 75th percentiles, minimum and maximum. No statistical tests will be performed.

A line graph will be produced for each analyte which displays the mean change from baseline value by week.

Laboratory toxicity will be graded using Adverse Event Severity Grading Tables when possible. The worst laboratory toxicity grade during treatment for each laboratory parameter within each laboratory category (hematology, liver function, chemistries, urinalysis and immunoglobulins) will be presented.

Toxicity grade shifts from baseline of  $\geq 2$  grades will be summarized during treatment for each laboratory parameter within each laboratory category (hematology, liver function, chemistries, urinalysis and immunoglobulins). The table will display the number and percentage of subjects with at least one  $\geq 2$  grade shift as well as the specific shift categories: Grade 0 to 2, Grade 0 to 3, Grade 0 to 4, Grade 1 to 3, Grade 1 to 4 and Grade 2 to 4.

For laboratory tests without toxicity grades within each laboratory category (hematology, liver function, chemistries, urinalysis and immunoglobulins), shifts relative to the normal range will be summarized for each analyte as shifts 'to low' and shifts 'to high'. For the 'to low category' the percentage of subjects with at least one low post-baseline value, including unscheduled visits, in the study period relative to baseline will be displayed using the categories: no shift to low and normal/high to low. For the 'to high category' the percentage of subjects with at least one high post-baseline value in the study period relative to baseline will be displayed using the categories: no shift to high and normal/low to high. No statistical tests will be performed.

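### The laboratory grade-shift table cannot show a Grade 3 to 4 worsening, although the entry criteria allow stable Grade 3 values for five parameters

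*SAP*

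**What the plan says.** SAP 4.3.3.1 (Laboratory Data) plans two summaries based on toxicity grade.

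- **Worst grade.** "The worst laboratory toxicity grade during treatment for each laboratory parameter within each laboratory category" is to be presented. The text does not mention baseline grade here.
- **Shift table.** "Toxicity grade shifts from baseline of" two grades or more are summarised during treatment. The table gives the number and percentage of subjects with at least one such shift. It then breaks these down into six rows: three that start from Grade 0 (ending at 2, 3 or 4), and after them "Grade 1 to 3, Grade 1 to 4 and Grade 2 to 4".

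The same section also plans weekly values and change from baseline for each analyte, including minimum and maximum, and a listing of all laboratory data.

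Protocol 5.2, exclusion criterion 5, bars laboratory abnormalities of Grade 3 or higher, with exceptions. Those that matter here are:

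- "Stable Grade 3 neutropenia; or stable Grade 3 lymphopenia; or stable Grade 3 leukopenia, due to SLE"
- "Stable Grade 3 hypoalbuminemia due to lupus nephritis and not related to liver disease or malnutrition"
- "Stable Grade 3 gamma glutamyl transferase (GGT) elevation due to lupus hepatitis" (subject to further conditions)
- "Any grade proteinuria"

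Protocol 10.2.1 grades laboratory values up to Grade 4, which is headed as potentially life-threatening.

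**The concern.** A two-grade rule suits a population that starts at Grade 0 to 2. This trial deliberately admits some children at Grade 3, where only one step remains. For a parameter that is Grade 3 at baseline, a move into the most severe grade falls outside the shift table, while a move from Grade 0 to Grade 2 falls inside it.

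The shift table is the only planned summary that sets on-treatment grade against baseline grade. That comparison matters because every child arrives after 48 weeks of IV belimumab, and the safety estimand in SAP 4.3 aims at on-treatment effects likely to be attributable to the drug. Three of the five parameters are white-cell counts. Infection is the first risk in Protocol 2.3.1, whose mitigation column names Grade 3 or greater neutropenia, lymphopenia and leukopenia.

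**Working it through.** **1. Reproduce the SAP's list.** Grades run from 0 to 4. The possible upward shifts are 0–1, 0–2, 0–3, 0–4, 1–2, 1–3, 1–4, 2–3, 2–4 and 3–4: ten in all. Those of two grades or more are 0–2, 0–3, 0–4, 1–3, 1–4 and 2–4. These six are exactly the SAP's categories, so the list is complete under its own rule.

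**2. Worsenings that the table can show, by baseline grade.**

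| Baseline grade | Possible worsenings | Shown now | Shown with 3–4 added |
|---|---|---|---|
| 0 | 4 | 3 | 3 |
| 1 | 3 | 2 | 2 |
| 2 | 2 | 1 | 1 |
| 3 | 1 | 0 | 1 |
| 4 | 0 | – | – |

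The largest worsening from Grade 3 is 4 − 3 = 1, which is below the threshold of 2. Grade 3 is the only baseline grade that can still worsen but has no worsening in the table. The change takes the list from six categories to seven.

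**3. Illustration with the neutrophil thresholds in Protocol 10.2.1** (Grade 2: 1000–1499/mm³; Grade 3: 500–999/mm³; Grade 4: below 500/mm³). The patient values are hypothetical.

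- Child A goes from 800 to 400/mm³, Grade 3 to 4. Contribution to the shift table: 0. Change from baseline: 400 − 800 = −400.
- Child B goes from 4500 to 1400/mm³, Grade 0 to 2. Contribution to the shift table: 1. Change from baseline: 1400 − 4500 = −3100.

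The change-from-baseline summary includes both children, but its mean and minimum are driven by B, not by the child who reached Grade 4.

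**4. Can the event be recovered from the other grade table?** For one parameter, take the number of children with worst grade 4 and subtract those in the 0–4, 1–4 and 2–4 rows. The remainder had a baseline of Grade 3, Grade 4 or missing. Grade 4 at entry is not allowed for the five parameters, so the remainder would usually be the 3–4 cases. This is an inference, though. SAP 4.1.2 takes the latest pre-dose value as baseline, and the schedule of activities has separate screening and Day 1 laboratory assessments, so the baseline grade can differ from the grade at screening.

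**5. Size.** The planned sample is 17, so one child is 1/17 = 5.9%. If only the 14 children of the precision calculation remained, it would be 1/14 = 7.1%. The documents do not say how many children will enter at Grade 3, so no rate within that group can be computed.

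**The case against.** A reader might infer that a Grade 3 to 4 worsening is never counted at all. The documents do not support that. The worst-grade table counts every on-treatment Grade 4 value in a graded parameter, the numerical change enters the change-from-baseline summaries, and every value is listed. With about 17 children, a reader of the listing can trace a Grade 4 value back to its baseline.

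Nor is a row missing by mistake: the six categories are complete under the two-grade rule. The request is for a different rule in a purely descriptive study, and the documents attach no decision to this table. It would also be wrong to say that the worst-grade table hides these cases among children who entered at Grade 4. For the five parameters only stable Grade 3 is excepted, so apart from drift before Day 1 or an eligibility deviation, an on-treatment Grade 4 is new.

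Proteinuria, where any grade may enter, looks like a stronger example but is a weak one. Table 3 of Protocol 10.2 requires dipstick protein and microscopy, without a protein:creatinine ratio or 24-hour protein. On the dipstick scale Grade 4 is nephrotic syndrome, which is not a dipstick reading, and the SAP grades only when possible.

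These objections stand, and they make the point minor. They do not supply a baseline-referenced grade summary. The adverse-event route does not fully replace one either. Protocol 8.3.4 has clinically significant changes recorded as AEs, but Protocol 10.3.1 leaves out abnormal findings associated with the underlying disease unless the investigator judges them more severe than expected. The Grade 3 values admitted here are those attributed to SLE, lupus nephritis or lupus hepatitis, so this route rests on investigator judgement for exactly these parameters.

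**Conclusion.** The point holds as a limitation of one table. For neutrophils, lymphocytes, leukocytes, albumin and GGT, the shift table cannot show the only grade worsening open to a child whose baseline is an allowed Grade 3, and no other planned summary links the resulting Grade 4 to that baseline. It does not extend to the claim that such worsening goes unreported, or that these children have no visible worsening: numerical change in the same parameter and grade shifts in their other parameters are still summarised.

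The severity is minor. The analysis is descriptive, the primary PK endpoint is unaffected, and the number of children concerned is unknown and may be zero. One such child would be 5.9% of 17. The conclusion assumes that the worst-grade table is produced as SAP 4.3.3.1 describes it, without a breakdown by baseline grade.

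**What to change.** In SAP 4.3.3.1:

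1. Add *Grade 3 to 4* to the shift categories.
2. Count it in the summary row for at least one shift, and retitle that row *shift of ≥2 grades or any shift to Grade 4*. Shifts to Grade 4 from Grades 0, 1 and 2 already qualify, so 3–4 is the only category this adds.
3. Present worst on-treatment grade cross-tabulated by baseline grade for each graded parameter, so that unchanged Grade 3 values are separated from worsening.

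This would be in keeping with the same section's treatment of immunoglobulins, which repeats the summary for subjects at or above the lower limit of normal at baseline.

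The cost is one row and one table from data already collected, with no extra samples or visits and no change to any clinical rule. The downside is that the summary row no longer follows the pure two-grade rule and its count may be slightly higher.

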#### **4.3.3.2. Vital Signs**

Vital signs assessment including 12-week on-treatment period and 8-week post-treatment follow-up period will be included in the analysis.

A summary of vital signs and change from baseline of vital signs will be presented by week. A listing of all subjects' vital signs will be presented.

## 4.4. Other Analyses

### 4.4.1. Subgroup analyses

Subgroup analyses of clinical interest will be made by the following subgroups:

- Baseline Body Weight:  $\geq 50$  kg vs  $\geq 30$  kg -  $< 50$  kg vs  $15$  kg -  $< 30$  kg

## 4.5. Interim Analyses

No formal interim analyses are planned.

## 4.6. Changes to Protocol Defined Analyses

There were no changes or deviations to the originally planned statistical analysis specified in the protocol amendment 02(approval date of protocol: 24 Jan 2024).

## 5. SAMPLE SIZE DETERMINATION

There are no formal calculations of power for this study. The sample size justification for study 217091 is based on the precision in the estimate of the geometric mean of  $C_{avg,ss}$ , over all study participants. The coefficient of variation (CV) for between-subject variability in  $C_{avg,ss}$  was approximated to 35.5%, equal to the variability evaluated in overseas children receiving belimumab IV in study BEL114054 [Dimelow, 2020], on the basis that bioavailability for SC dosing is similar in all subjects and does not significantly increase variability in exposure.

$C_{avg,ss}$  is expected to be log-normally distributed and the 95% confidence interval (CI) relative to the geometric mean is given by  $\exp(\pm t_{97.5, N-1} \times sd / \sqrt{N})$ , where  $t_{97.5, N-1}$  is the 97.5th percentile of the t-distribution with  $N-1$  degrees of freedom,  $sd$  is the standard deviation in the logarithm of  $C_{avg,ss}$  equal to 0.345 for 35.5% CV, and  $N$  is the number of subjects.

For  $N$  of 14, the 95% confidence interval in  $C_{avg,ss}$  relative to the geometric mean is 82% to 122%. The 95% CI therefore lies within 22% of the point estimate for  $C_{avg}$  and this level of precision is considered adequate to characterize belimumab exposure in Chinese children receiving belimumab SC.

Considering the withdrawal rate in the previous and ongoing Benlysta paediatric studies in overseas and China, the withdrawal rate in the current study is estimated to be 20%. To account for a 20% withdrawal rate, the total sample size is 17.

## 6. SUPPORTING DOCUMENTATION

### 6.1. Appendix 1 Study Population Analyses

The ITT population will be used to summarize the study population data.

#### 6.1.1. Participant Disposition

The number and percentage of subjects enrolled by site will be summarized.

Using the Screened population, the number of subjects in each population (Screened, Enrolled, ITT and PK) will be summarized. A summary of the reasons for the screen failures will be provided along with a listing of the subjects who were screen failures.

If there are any subjects who are enrolled but do not receive any study drug, they will be included on the subject disposition listing in the Enrolled population, but not the ITT population.

For the ITT population, the subject's completion status will be assessed to evaluate percentages of dropouts as well as the reasons for dropout. The number and percentage of subjects who completed through Week 12 and who withdrawal, including reasons for withdrawal, will be displayed. Additionally, the cumulative number and percentage of subjects who withdrew by study visit based on different body groups will be displayed. The number and percentage of subjects who complete study and who withdrew, including reasons for withdrawal, will be displayed. The number and percentage of subjects who complete study intervention and who withdrew, including reasons for withdrawal, will be displayed.

A listing of subjects that deviated from the inclusion or exclusion criteria will be provided.

A listing of subject disposition will be provided showing their completion status and whether or not they are included in each population. A listing of subjects who withdrew from the study, including reason for withdrawal will also be provided.

#### 6.1.2. Demographic and Baseline Characteristics

Descriptive statistics will be used to summarize the continuous demographic and baseline characteristics of age (years), height (cm), weight (kg), body mass index (BMI) (kg/m^2) and vital signs (blood pressure). Counts and percentages of the following categorical demographic and baseline characteristics will be presented: sex, Hispanic or Latino origin, race, body weight group ( $\geq 50$  kg,  $\geq 30$  kg -  $< 50$  kg and 15 kg -  $< 30$  kg). A summary of the number and percentage of subjects reporting each general medical history term will also be provided.

The summary of demographic and baseline characteristics, general medical history will be repeated for the following subgroups, where the subgroup categories are defined as:

- Baseline Body Weight:  $\geq 50$  kg vs  $\geq 30$  kg -  $< 50$  kg vs 15 kg -  $< 30$  kg

Demographics will be listed for all patients.

Allowable SLE medication usage— counts and percentages by class (Steroids, Anti-malarials, Nsaids, Other Immunosuppressive/Immunomodulatory Agents and Aspirin) at baseline will be summarized.

### **6.1.3. Protocol Deviations**

Important protocol deviations will be summarized.

Protocol deviations will be tracked by the study team throughout the conduct of the study. These protocol deviations will be reviewed to identify those considered as important as follows:

- Data will be reviewed prior to freezing the database to ensure all important deviations are captured and categorized in the protocol deviations dataset.
- This dataset will be the basis for the summaries of important protocol deviations.

The percentage of subjects who experience an important protocol deviation will be presented. The tables will display the number and percentage of subjects who experience any important protocol deviation and for each deviation type. A listing of subjects experiencing an important protocol deviation will be provided.

A separate summary of all inclusion/exclusion criteria deviations will also be provided.

### **6.1.4. Prior and Concomitant Medications**

Prior medication is any medication that started before first dose of study treatment. Concomitant medications include any medication that was taken at some point during the study period (post first dose of study treatment), regardless of whether it was started prior to the first dose of study treatment or not.

Concomitant medications will be coded according to drug name as defined in the WHO Drug Dictionary, and classified according to the WHO-Drug ATC classification level 1 and ATC level 4. A summary of the number and percentage of subjects with concomitant medications by ATC level 1 term and ATC level 4 term will be displayed. A further summary of concomitant medications by ATC level 4 term and preferred term will be provided. A listing of all concomitant medication data will be displayed by subject.

The number and percentage of subjects who receive protocol-prohibited medication will be summarized.

A listing of protocol-prohibited medication will be displayed by subject.

Additionally, a summary of concomitant medications by ATC level 1 term and ATC level 4 term used 12 weeks on treatment period summary of concomitant medications by ATC level 4 term used 12 weeks on treatment period will be displayed.

## 6.2. Appendix 2 Data Derivations Rule

### 6.2.1. Study Period

Assessments and events will be classified according to the time of occurrence relative to the study intervention period.

Treatment period	Definition
Pre-Treatment	Event start date < IP start date
On-Treatment	IP start date ≤ Event start date ≤ Week 12 Date or Early Withdrawal Date
Post-Treatment	Event start date > Week 12 Date or Early Withdrawal Date

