2. The 16-week follow-up requires a phone call to collect adverse events (AEs) and the results of home urine pregnancy test (if applicable) for female participants. The 16-week follow-up may be performed at a clinic visit per local requirement.
3. Full Physical Examination is required at screening. An abbreviated/symptom-driven exam can be done thereafter as described in Section 8.3.1.
4. Serum pregnancy test required at screening for all females of childbearing potential. Urine pregnancy test is sufficient for all subsequent visits. A home pregnancy test (urine) will be provided to participants for the 16-week follow-up pregnancy assessment.
5. Laboratory assessments in visit 1 (screening) and visit 2 (Day 1) would share with study 213560 visit 16 (Week 48) and visit 17 (Week 52) laboratory assessments respectively.
6. The participant's weight at Day 1 should be calculated to decide dosing frequency for each following visit to be administered.
7. For those participants who don't have IV PK samples in study 213560, 3 additional PK samples will be collected within 4 hours, at 7 days (± 2 days) and 14 days (± 2 days) after last belimumab IV infusion at week 48 of study 213560.
8. Samples must be taken pre-dose.
9. For the first 2 doses participants must be observed for 3 h post belimumab injection. 10. If the PK sample collection on visit 3 was missed, then that PK sample collection should be rescheduled at 3 ± 1 day after any of the next doses.
11. If the PK sample collection on visit 4 was missed, then that PK sample collection should be rescheduled to when participants take the next dose and the sample must be taken pre-dose.

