#### 4.1.2. Baseline Definition

For all endpoints the baseline value will be the latest pre-dose assessment with a non-missing value, including those from unscheduled visits. If time is not collected, Day 1 assessments are assumed to be taken prior to first dose and used as baseline.

Unless otherwise stated, if baseline data is missing no derivation will be performed and baseline will be set to missing.

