**6.2.4. Multiple measurements at One Analysis Time Point**

For lab tests on a study day, if more than one assessment is taken on the same day, the test from a central lab will be taken over the test from a local lab. If multiple assessments are taken from the same type of lab, the worst case will be used.

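### A Day 1 pre-dose laboratory result is both baseline and On-Treatment, so the worst-grade table counts abnormality present before the first SC injection

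*SAP*

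**What the plan says.** SAP 6.2.1 gives the period rule and applies it to laboratory assessments as well as to events: "Assessments and events will be classified according to the time of occurrence relative to the study intervention period". Pre-Treatment is "Event start date < IP start date". On-Treatment is "IP start date ≤ Event start date ≤ Week 12 Date or Early Withdrawal Date". Both are comparisons of dates. There is no time of day and no exception for a sample taken before the injection.

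SAP 4.1.2 defines baseline: "For all endpoints the baseline value will be the latest pre-dose assessment with a non-missing value, including those from unscheduled visits". Where no time is recorded, "Day 1 assessments are assumed to be taken prior to first dose and used as baseline".

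SAP 4.3.3.1 plans a table of "The worst laboratory toxicity grade during treatment for each laboratory parameter within each laboratory category". The same section plans a table of toxicity-grade shifts of at least 2 grades from baseline, also during treatment. Neither description says post-baseline. Two other outputs in that section do: the change-from-baseline summaries, and the reference-range shifts for tests without grades.

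SAP 6.2.4 handles several results on one study day. A central laboratory result is taken over a local one, and then "If multiple assessments are taken from the same type of lab, the worst case will be used". Day 1 and baseline are not excepted.

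The protocol's Schedule of Activities puts haematology, chemistry, urinalysis and immunoglobulins on Day 1 in all three weight groups. Footnote 5 says that the screening laboratory tests and those of "visit 2 (Day 1) would share with study 213560 visit 16 (Week 48) and visit 17 (Week 52) laboratory assessments respectively". The Day 1 sample is thus the Week 52 sample of the IV study.

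**The concern.** One laboratory result has two roles. Under 4.1.2 it is the pre-dose reference; under 6.2.1 it belongs to the treatment period that is compared with that reference. A table described as showing the worst grade during SC treatment then includes grades that existed before any SC drug was given.

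This matters because children may enter with abnormal values. Exclusion criterion 5 (protocol 5.2) allows any grade of proteinuria, certain stable Grade 3 findings and Grade 1-2 values generally. All participants have also had 48 weeks of IV belimumab, and protocol 2.2.4 reports falls in immunoglobulins on the IV form in children. Immunoglobulins are in this table. There is no control arm against which an inflated grade could be judged.

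The second issue is narrower. If two Day 1 results exist, 4.1.2 points to the latest and 6.2.4 to the worst. The shift table can depend on which rule the programmer applies.

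**Working it through.** The documents give no figure to reproduce. The check applies the rules to cases.

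**Step 1. Period by date (SAP 6.2.1).** Take the first injection as Day 1 and the Week 12 date as Day 85.

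- Day -1: before the start date, so Pre-Treatment.
- Day 1, pre-dose: on the start date, so On-Treatment.
- Day 29 and Day 85: On-Treatment.
- Day 86: Post-Treatment.

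A sample drawn the day before the injection is excluded from the treatment period. The same sample drawn on the morning of the injection is included.

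**Step 2. Is a same-day draw the expected case?** Protocol 2.2.5 places the last IV dose at Week 48 (Day 336). The Week 52 assessment falls nominally at 52 - 48 = 4 weeks after it. Protocol 4.1 requires completion of the Week 52 assessment and a first SC dose no more than 4 weeks after the last IV dose. On nominal timing, both fall on the same day. The visit windows of study 213560 are not in the documents, so the share of children with an earlier-dated sample is unknown.

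**Step 3. Worst-grade table.** Grades come from protocol 10.2.1: dipstick protein 1+ is Grade 1, 2-3+ is Grade 2 and 4+ is Grade 3. Take a child with 4+ on Day 1 before the injection and 1+ at every later visit.

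- As written: max(3, 1, 1, 1) = Grade 3 during treatment.
- Post-baseline only: max(1, 1, 1) = Grade 1.

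The tabulated grade can never be below the Day 1 grade when the sample is dated Day 1. If 17 children are treated, each child who enters abnormal and improves moves 1/17 = 5.9 percentage points into a grade not reached after the first injection.

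**Step 4. Shift table without duplicates.** The Day 1 value compared with itself is a shift of 0. The overlap of periods alone changes nothing here.

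**Step 5. Shift table with unequal Day 1 duplicates of one laboratory type.** Let *a* be the earlier grade, *b* the latest and *p* a later on-treatment grade, each 0 to 4, with *a* ≠ *b*.

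- Baseline = latest (4.1.2): a shift is counted when *p* - *b* ≥ 2. For each *b* there are 4 values of *a*. The qualifying values of *p* number 3 for *b* = 0, 2 for *b* = 1 and 1 for *b* = 2. Total: 4 × (3 + 2 + 1) = 24 combinations.
- Baseline = worst (6.2.4): a shift is counted when *p* - max(*a*, *b*) ≥ 2. Of the 24, 3 remain for *b* = 0, 3 for *b* = 1 and 2 for *b* = 2, which is 8. So 24 - 8 = 16 are lost, and none is added.
- Example: neutrophils of 1,450 (Grade 2) then 1,550/mm³ (Grade 1) on Day 1, later 700/mm³ (Grade 3). The latest-value baseline gives 3 - 1 = 2, which is counted. The worst-value baseline gives 3 - 2 = 1, which is not.
- The reverse error: if 4.1.2 sets baseline but the earlier, worse Day 1 value stays in the On-Treatment set, a false shift is counted when *a* - *b* ≥ 2. There are 6 such pairs: (2,0), (3,0), (3,1), (4,0), (4,1) and (4,2).

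These are counts of possible combinations, not expected frequencies in patients.

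**The case against.** The strongest reply is that the literal reading is not the natural one. The rows of 6.2.1 speak of an event start date, 4.1.2 treats untimed Day 1 values as pre-dose, and a programmer would not ordinarily call a pre-dose value on-treatment. That may be what was meant. But the opening sentence of 6.2.1 names assessments, no other period definition in the SAP covers them, and the design overview in SAP 1.1 starts the treatment period at Day 1. Other outputs in 4.3.3.1 carry the post-baseline limit that this table lacks.

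The second reply is that little follows. The error overstates toxicity rather than concealing it. A stable abnormality that persists gives the same worst grade either way, so the effect needs improvement on treatment. The SAP also plans weekly values, changes from baseline, post-baseline reference-range shifts and full listings. All of this stands, and it limits the weight of the point.

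A reader might go further and infer that the SAP makes the worst duplicate the baseline and so hides worsening. The documents do not support that. SAP 4.1.2 names the latest pre-dose value for all endpoints, and 6.2.4 first prefers central over local and never mentions baseline. No Day 1 duplicate is scheduled. Even in the neutrophil example, the 700/mm³ value still appears as Grade 3 in the worst-grade table and in the listings. What remains is a conflict between two rules without stated precedence.

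A reader might also illustrate the point with Grade 4 proteinuria. Protocol Table 3 schedules a dipstick, on which a reading alone reaches at most Grade 3.

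**Conclusion.** The point holds for the worst-toxicity-grade table. Followed as written, the SAP counts a pre-dose Day 1 grade as a grade during SC treatment whenever the sample is dated on the day of the first injection, which is the nominal schedule. The effect is 5.9 percentage points per affected child, assuming 17 treated. The number affected cannot be derived from the documents and may be zero. A shared Week 52 sample dated before the injection is correctly Pre-Treatment; the fault is that the table then depends on visit timing.

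The duplicate issue is secondary. It arises only for same-day Day 1 results from the same type of laboratory that differ in grade, which I assume to be uncommon. The error could go either way: lost shifts if 6.2.4 is applied to baseline, or false shifts if 4.1.2 governs and the worse value stays in the On-Treatment set.

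It would be wrong to infer that the trial's main results are at risk. Only descriptive laboratory tables are affected. The PK endpoint and the adverse event, SAE and AESI summaries do not use these laboratory rules. The change is still worth making because it corrects a stated rule at almost no cost.

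**What to change.** Make three wording changes to the SAP:

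- **6.2.1:** state that laboratory results on the IP start date that were taken before the first injection, or that carry no time, are baseline and Pre-Treatment.
- **4.3.3.1:** limit the worst-toxicity-grade table and the toxicity-grade shift table to post-baseline values during treatment, as the reference-range shifts already are.
- **6.2.4:** state that 4.1.2 governs the choice of baseline and that the worst-case rule applies only to post-baseline days. Add a tie rule for untimed Day 1 duplicates, for which no latest value can be identified.

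The cost is a short SAP amendment and one flag in the laboratory analysis dataset. No data collection, visit or sample changes.
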